#### Third, what tests should we use to assess efficacy?

If YF476 has a marked effect on gastric carcinoids, visual inspection of the tumours at gastroscopy might be enough to assess efficacy in some patients, but we will also take biopsies for histological and biomarker assessments, blood samples to assay fasting serum gastrin and plasma CgA, and trough and peak serumYF476.

#### Fourth, what should be the study design?

A placebo-controlled trial of a new type of therapy for gastric carcinoids such as YF476 would be the ideal study design. However, the proposed outcome measures are robust enough to assess efficacy in an open trial without a comparator.

#### Fifth, should we study women as well as men?

Atrophic gastritis is more common in women than men. YF476 is not teratogenic. So, post-menopausal women or pre-menopausal women using a reliable method of contraception (but not a steroid, which is metabolised via CYP3A4; see Appendix 1) will be eligible.

#### Sixth, should we exclude H. pylori-positive subjects?

Excluding *H. pylori* positive patients would restrict recruitment. We know of no evidence that *H. pylori* infection influences development of gastric carcinoids in humans, so we will test patients for *H. pylori* at screening but not exclude positive subjects. Also, we will assess the impact of infection on the outcome of YF476 treatment.

Seventh, what are the potential risks of harm to the trial subjects from YF476 and from the trial procedures, and how might they be mitigated?

#### *i)* Prolongation of QTc interval of the ECG?

YF476 appears to have low potential for prolonging QT interval, a risk factor for torsade de pointes (see Section 7.8.4). But, until we have more information about YF476, patients with prolonged QT interval should be excluded from clinical trials.

#### *ii)* Drug-drug interaction?

There is only a remote likelihood of an interaction in patients between YF476 and a drug metabolised through CYP1A2, CYP2B6, CYP2C19, CYP2D6 and CYP2C9 (see Section 7.8.4).

The FDA recommends that, if the [I]/Ki ratio for a CYP enzyme is >0.1 at the highest proposed clinical dose, an interaction study in healthy subjects should be done, or concomitant medication should be restricted appropriately. Currently, the highest

proposed clinical dose of YF476 is 50–100 mg once daily. [I]/Ki ratios are >0.1 for CYP2C8 at YF476 doses of >50 mg and for CYP3A4 at YF476 doses of >100 mg. So, in this study, restriction is required of concomitant medication metabolised by CYP2C8 and possibly also by CYP3A4.

Few drugs are metabolised via CYP2C8, and they are unlikely to be co-administered with YF476. So, it is better to restrict the use of such drugs in early studies of YF476 in patients, rather than carrying out a study of CYP2C8 in vivo.

About 60% of drugs are metabolised via CYP3A4, so that enzyme is more important than CYP2C8. If the therapeutic dose of YF476 proves to be >50-100 mg daily, a study of CYP3A4 in vivo will be done. That will be a study to assess the effect of YF476 on the pharmacokinetics of oral midazolam – a CYP3A4 substrate – in healthy subjects. Meanwhile, only drugs that are metabolised via CYP3A4, and have a wide therapeutic window, may be co-administered with YF476 at the proposed doses in this study.

For guidance, medicines that inhibit or induce CYP3A4/5 and CYP2C8 are listed in Appendix 1.

Concomitant treatment will be allowed during the proposed trial only if necessary (see Appendix 1). Healthy subjects who were sedated with *intravenous* midazolam before gastroscopy in a recent study (HMR code: 05-021) tolerated it as well after 6 weeks' treatment with YF476 as they tolerated it before baseline gastroscopy (see Section 7.8.5). Therefore, should they wish, patients can be sedated with intravenous midazolam safely before gastroscopy in the proposed trial.

#### iii) Endoscopy?

Patients who take part in the proposed trial must undergo up to four gastroscopies. All patients will have had at least one gastroscopy before the trial. Most gastroscopies are done without any problem. Some people have a sore throat for a day or so afterwards. Patients may feel tired or drowsy for several hours after midazolam. There is a slightly increased risk of developing a chest infection after gastroscopy. Occasionally, the endoscope damages the gut and causes bleeding, infection, and rarely, perforation.

#### Finally, what are the potential benefits to patients compared with the risk of harm?

Troublesome gastric carcinoids are usually dealt with surgically (Dakin *et al* 2006). Surgery does not always work and carries a risk of harm. Octreotide – a somatostatin analogue –has also been used to treat patients with type I carcinoids (Fykse *et al* 2004 and 2005). Octreotide has to be given by injection and is not that effective, probably because it is not selective for the gastrin receptor. YF476 is active by mouth and seems to be better tolerated than somatostatin analogues. Therefore, YF476 offers significant benefit over existing treatments for gastric carcinoids.

Overall, the potential benefits to the trial subjects of taking part in the trial greatly outweigh any risks of harm.

#### 8 Objectives

The primary objective of this pilot study is:

• to assess if YF476 is an effective medical treatment for type I gastric carcinoids.

*The secondary objectives are:* 

- to assess the tolerability and safety of YF476; and
- to assess the effect of YF476 on plasma concentration and transcript profiles of biomarkers such as chromogranin A (CgA).

#### 9 Overall trial design

Patients will attend the clinic up to 12 times. The time that patients take to complete the trial will depend on their response to YF476.

At Visit 1, patients will be screened (excluding gastroscopy) for eligibility.

At **Visit 2**, patients will undergo gastroscopy and gastric biopsies. If they meet all the inclusion/exclusion criteria, they will start treatment with 50 mg YF476 by mouth *once* daily at home on the next day. Each subject will be given a unique number at the start of treatment.

They will complete a diary card daily throughout the treatment period.

**Visit 3** will be 3 weeks after starting YF476, to assess tolerability, safety and blood levels of gastrin, CgA and YF476.

**Visit 4** will be 6 weeks after starting YF476, to assess tolerability and safety, to repeat the gastroscopy and gastric biopsies, and to take blood samples to assess levels of gastrin, CgA and YF476. If the gastric carcinoids have regressed completely on visual inspection, YF476 will be stopped, Visits 5 and 6 will be omitted, and the patient will proceed to Visit 7. If the gastric carcinoids are still present, YF476 will be continued, but the dose may be increased to 75 or 100 mg *once* daily, at the discretion of the investigator.

**Visit 5** will be 9 weeks after starting YF476, to assess tolerability, safety and blood levels of gastrin, CgA and YF476.

**Visit 6** will be 12 weeks after starting YF476, to assess tolerability and safety, to repeat the gastroscopy and gastric biopsies, and to take blood samples to assess levels of gastrin, CgA and YF476. If the carcinoids have not regressed, the patient will leave the trial. If the carcinoids have regressed, the patients will proceed to Visit 7.

**Visit 7** will be a follow-up visit, 12 weeks after the end of treatment with YF476, only for patients who respond to YF476. The gastroscopy and blood sampling for fasting gastrin and CgA will be repeated.

#### **Extended treatment**

Some patients will be eligible for extended treatment with YF476, as described below. To be eligible for further treatment, the patient must have benefitted from 12 weeks' treatment, and have tolerated YF476 well, and must give fully informed written consent.

**Visit 8** will be to inform the patient about the extended dosing period and prescribe YF476 capsules. If the investigator thinks that a new baseline gastroscopy and blood sampling (for safety, gastrin and CgA) is necessary, this will be carried out.

**Visit 9** will be 12 weeks after starting extended treatment with YF476, to assess tolerability, safety and blood levels of gastrin, CgA and YF476.

**Visit 10** will be 24 weeks after starting extended treatment with YF476, to assess tolerability and safety, to repeat the gastroscopy and gastric biopsies, and to take blood samples to assess blood levels of gastrin, CgA and YF476.

**Visit 11** will be 36 weeks after starting extended treatment with YF476, to assess tolerability, safety and blood levels of gastrin, CgA and YF476.

**Visit 12** will be 52 weeks after starting extended treatment with YF476, to assess tolerability and safety, to repeat the gastroscopy and gastric biopsies, and to take blood samples to assess levels of gastrin, CgA and YF476.

A formal follow-up visit will be omitted, as the patients are closely followed by the investigator as part of their standard healthcare.

The end of the trial will be the last visit by the last subject.

#### 10 Trial population

#### 10.1 Planned number of subjects

Up to 10 eligible men or women will complete the trial.

#### 10.2 Inclusion criteria

- 1. Patients known to have gastric carcinoids associated with chronic atrophic gastritis and hypergastrinaemia and who attend the out-patient clinic of the principal investigator.
- 2. Men; post-menopausal women; pre-menopausal women who have been sterilised by tubal ligation, hysterectomy or bilateral oophorectomy; or pre-menopausal

women using one of the allowed methods of contraception: condom and spermicide or intra-uterine device.

- 3. Adults  $\geq 18$  years.
- 4. Good general health.
- 5. Able to give fully-informed, written consent.

#### 10.3 Exclusion criteria

- 1. Women who are pregnant, lactating or using a steroid contraceptive.
- 2. History of gastric surgery, apart from surgery for gastric carcinoids.
- 3. Evidence of Zollinger-Ellison syndrome.
- 4. Prolonged QTc interval (> 450 msec).
- 5. Certain medicines and herbal remedies (see Appendix 1) taken during the 7 days before Visit 1.
- 6. Previous treatment with somatostatin analogues.
- 7. Participation in a clinical trial of an unlicensed medicine within the previous 3 months.

#### 10.4 Withdrawal of subjects from the trial

Subjects are free to withdraw from the trial at any time without giving reasons. Furthermore, the investigator may withdraw a subject for medical reasons such as intolerance to trial medication, intercurrent illness, need for medication which is contraindicated, lack of efficacy of trial medication, or withdrawal of consent. The investigator will assess reasons for withdrawal as far as possible and will fully record the circumstances and medical details.

Subjects will be informed before they agree to take part in the trial that, if they withdraw:

- the investigator will stop collecting information about them; and
- they can ask the investigator to destroy any identifiable samples taken from them.

The investigator will ask withdrawn subjects to return unused trial medication, and to consent to a follow-up examination, to check that they have come to no harm as a result of taking part in the trial. Provided that subjects agree, they will undergo, at withdrawal from the trial, the standard medical examination and laboratory tests which they would have undergone had they completed the treatment regimen. The investigator will record in the CRF the results of the follow up examination of withdrawn subjects, if they give their consent for that.

For the extended treatment period, the following criteria apply:

Patients will be withdrawn from the study if they:

- have ALT or AST values >3 times the upper limit of normal;
- are found to have a prolonged QTc value (QTc ≥ 500 ms or QT prolongation with an increase of QTc > 60 ms compared to baseline);
- show any evidence of suspected drug-drug interaction; or
- experience an SAE or SUSAR which can reasonably be attributed to YF476.

If one of the criteria above is met in 2 or more subjects, dosing will be stopped in all subjects.

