# 16.4 Procedures for handling withdrawals due to adverse events

The investigator will assess the reason for withdrawal as far as possible and will fully record the circumstances and medical details. Provided that subjects give written informed consent, they will undergo the standard medical examination and laboratory tests at withdrawal from the trial which they would have undergone had they completed it (see also Section 10.4).

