# Safety data

Data from all subjects who received any trial treatment will be included in the analysis of safety.

Numerical data will be summarised using means or medians, and other descriptive statistics, according to the type and distribution of the data. Adverse events (see Section 16) will be listed and relationship to treatment assessed.

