- (h) If after the first few patients have completed the trial it is clear that increasing the dose at Visit 4 from 50 mg YF476 *once* daily to 75 or 100 mg *once* daily is necessary for a satisfactory response, and that the regimen is well tolerated, subsequent patients may be started on 75 or 100 mg *once* daily at their next visit.
- (i) If after the first few patients a satisfactory response to the 50 mg YF476 dose once daily is seen at Visit 4, the dose may be reduced to 25 mg YF476 once daily, and subsequent patients may be started on this lower dose.

- (j) Follow-up may be extended if:
  - (i) a subject has an unresolved adverse event, which, in the opinion of the investigator, merits further follow-up; or
  - (ii) new information becomes available that supports an extended follow-up period.

The investigator will decide on the nature of the follow-up. For example, subjects may have a telephone follow-up at which they are asked about adverse events, or subjects may be asked to attend extra outpatient visits for additional monitoring of blood levels or effects of IMP, and for extra safety tests. The extra safety tests might include tests that are not described in this protocol. The investigator reserves the right, during or after the study, to do any extra safety tests that are in the best interest of the subjects. Those extra tests may or may not be described in this protocol.

(k) If the patient has not fasted for Visit 1, fasting safety tests of blood and urine may be done at Visit 2.

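### Section 10.4 merges stopping YF476 with leaving the trial, so no recording of the later course of a harm that led to withdrawal is required

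*Protocol*

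**What the plan says.** Section 10.4 covers several routes out of the trial under one heading. Subjects may leave freely, and "the investigator may withdraw a subject for medical reasons such as intolerance to trial medication". For the extended treatment period it adds mandatory criteria under the words "Patients will be withdrawn from the study if they": ALT or AST above three times the upper limit of normal, QTc prolongation, a suspected drug-drug interaction, or an SAE or SUSAR reasonably attributable to YF476.

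Between these two parts stands a paragraph of consent information, introduced by "Subjects will be informed before they agree to take part in the trial that, if they withdraw". Its first item is that "the investigator will stop collecting information about them". Its second is that subjects may ask for identifiable samples to be destroyed.

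On what is kept, section 10.4 says that the investigator "will fully record the circumstances and medical details", and section 16.4 repeats this for withdrawals due to adverse events. Section 16.4 continues: "Provided that subjects give written informed consent, they will undergo the standard medical examination and laboratory tests at withdrawal from the trial". Section 19 provides a separate consent form for this examination and lets the patient ask that its results stay out of the CRF.

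On analysis, section 18.1 (Safety data) states: "Data from all subjects who received any trial treatment will be included in the analysis of safety". Section 20.1(j) says that follow-up may be extended if "a subject has an unresolved adverse event, which, in the opinion of the investigator, merits further follow-up".

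**The concern.** Tolerability and safety is a secondary objective. For a liver or QTc finding, what happens after the drug is stopped (whether the abnormality peaks later, resolves or persists) is part of the evidence on whether the drug caused it. A protocol that defines no state of being off drug but still followed, and that links withdrawal to an end of data collection, risks losing that evidence in the patients who were harmed.

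The extension makes this more pressing. Section 7.9 says that the toxicology supports dosing for up to 13 weeks, and the longest completed dosing listed in section 7.8.5 is 6 weeks. The extension runs to 52 weeks, so harms seen there are largely new information. Section 10.4 also stops dosing in all subjects once a criterion is met in two or more, so the interpretation of each case carries weight.

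**Working it through.** The plan states no figure on this point, so the check is mainly a comparison of passages.

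**1. Does the protocol separate stopping drug from leaving the trial?** No. In section 10.4 intolerance leads to withdrawal of the subject, and the extension criteria lead to withdrawal from the study. The one exception to withdrawal is the Visit 4 or Visit 10 stop for complete regression, which is a response rule and not a safety rule.

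**2. Is the stop-collecting statement limited to withdrawn consent?** Not expressly. Its lead-in describes the subject's own act, but section 10.4 lists withdrawal of consent alongside intolerance among the reasons for which the investigator may withdraw a subject. Section 16.4, on withdrawals due to adverse events, refers back to 10.4 and makes the examination conditional on written consent. The text therefore leaves open whether the statement reaches a patient whom the investigator removes for toxicity.

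**3. What is recorded about a patient withdrawn for toxicity?**

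| Item | Section | Status |
|---|---|---|
| Circumstances and medical details | 10.4, 16.4 | Required |
| Adverse event onset, end and outcome | 16.2 | Required, but still present or not known is an accepted outcome |
| SAE form | 16.3 | Required for every SAE |
| Examination and laboratory tests at withdrawal | 10.4, 16.4, 19 | One occasion, with consent; the patient may keep results out of the CRF |
| Repeat laboratory safety tests | 20.1(b) | If the investigator has safety concerns |
| Up to 3 extra visits | 20.1(c) | Permitted, for technical failure or extra safety tests |
| Extended follow-up of an unresolved event | 20.1(j) | Permitted, on the investigator's opinion |
| Follow-up to resolution | none | Not required |
| Follow-up visit after extended treatment | 9 | Omitted; reliance on standard care |

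**4. Would the withdrawal examination show recovery?** Not reliably, because it is timed at withdrawal. It is also meant to match what the patient would have had on completing treatment. For the extension that is Visit 12, which section 14.12 describes as repeating Visit 8. Section 14.8 lists no ECG at Visit 8, while the notes in section 6.3 list one for Visit 12. Whether an ECG follows a QTc withdrawal is therefore unclear from the text.

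**5. Size.** Section 10.1 caps the trial at 10 patients. One incompletely followed patient among n treated is 1/n of the safety population. With n no greater than 10, 1/n is at least 1/10 = 10%. As a worst scheduled case, a patient withdrawn at Visit 9 (extension week 12) has 52 − 12 = 40 of the 52 scheduled weeks remaining. Withdrawal at a later visit leaves less.

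**The case against.** The strongest reply is that the stop-collecting line is consent information about a subject who chooses to leave. It is paired with that subject's right to have samples destroyed, and section 10.4 uses different grammar for action by the investigator. On that reading the line does not touch toxicity withdrawals and does not conflict with 20.1(j). This stands in part: applying the line to investigator withdrawals is an inference. It does not remove the point, because on the narrow reading there is still no passage that requires follow-up to resolution.

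A reader might infer that harms leading to withdrawal go unrecorded, or that recording ends at the moment of detection. The documents do not support that. The provisions in the table capture the event, its circumstances and an outcome category, and 20.1(b), (c) and (j) allow more. The withdrawal examination can also give a second value, since it follows the laboratory result that prompted it.

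A reader might also attach a probability that at least one of 10 patients is affected. No event rate for these patients is given, section 7.8.5 reports no effects on ECG or safety tests in healthy subjects, and the mandatory criteria apply only to the extension, which only some patients enter after having tolerated the drug. Such a figure would rest wholly on assumption.

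Lastly, 18.1 is not contradicted: withdrawn patients stay in the safety analysis. The tension is that membership of the analysis set cannot supply observations that nobody was required to collect.

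**Conclusion.** The point holds as a defect of wording with a real consequence for the safety data. Section 10.4 treats stopping YF476 and leaving the trial as one event, does not confine its stop-collecting statement to withdrawn consent, and leaves the course after withdrawal to one consent-dependent examination plus follow-up that depends on the investigator's judgement. An investigator could comply fully and still leave a liver or QTc event with no recorded resolution.

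Each such case is at least 10% of the safety population, given the cap of 10. How many cases to expect cannot be derived from the documents, and the 40-week figure is an upper case on the visit schedule, not a typical loss. The conclusion assumes that no other trial document, such as the information sheet, already draws the distinction. A later statistical analysis plan could not repair it, because the data would not have been collected.

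**What to change.** Reconcile sections 10.4, 16.4, 19 and 20.1(j) on two matters. First, state that data collection ends only for patients who withdraw consent to it. Second, state that for patients whose YF476 is stopped by the investigator, adverse-event outcome and safety data continue to be entered in the CRF, using the follow-up that 20.1(b), (c) and (j) already permit. Sections 14.12 and 6.3 should also agree on whether an ECG belongs to the final extension assessment.

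The stopping criteria, and the type and timing of clinical monitoring after stopping, stay for the sponsor to define. The cost is a protocol and information-sheet wording change and a little extra recording for patients who are off drug.

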#### 11 Treatments

#### 11.1 Treatments administered

Patients will take 50 mg YF476 by mouth once daily for up to 12 weeks. Investigators have the option to increase the dose to 75 or 100 mg *once* daily after 6 weeks' treatment (at Visit 4). If a satisfactory response is seen with 50 mg YF476 *once* daily after 6 weeks for the first few patients, subsequent patients may be started on 25 mg YF476 *once* daily.

For the extended treatment period, patients will receive the same daily dose of YF476 as they did at the end of the initial 12 week period. The investigator will still have the option to increase the patient's dose to 75 or 100 mg once daily, or reduce it to 25 mg, depending on progress.

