# 14.4 Visit 4: 6 weeks after starting YF476

The investigator will:

- check that the patient has fasted;
- collect the diary card, and issue a new one;
- check the diary card for compliance with treatment, and for adverse events and concomitant medication;
- collect YF476 container and assess compliance;
- do a medical examination, including blood pressure and heart rate measurements, and 12-lead ECG;

- collect blood and urine for safety tests, including a pregnancy test for women of child-bearing potential.
- collect blood for assay of fasting levels of gastrin, CgA, YF476 (trough), and serum for storage;
- do a gastroscopy and take gastric biopsies, and proceed as follows:
  - if on visual inspection the gastric carcinoids have regressed completely: stop YF476, omit Visits 5 and 6, and proceed to Visit 7, providing all safety assessments prove satisfactory; or
  - if on visual inspection gastric carcinoids are still present: continue 50 mg YF476 *once* daily or consider increasing the dose to 75 or 100 mg *once* daily, issue a third container of YF476 capsules (25 mg); issue a new diary card;
  - after collecting the fasting blood sample and doing the gastroscopy, give the patient their dose of YF476, wait 1 h, and then collect blood for assay of peak YF476 concentration; and
  - instruct the patient about Visit 5.

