# 18.2 Determination of sample size

The trial is an exploratory, open, pilot trial, so a power calculation is inappropriate. Gastric carcinoids are a rare condition, so the protocol sets a limit of up to 10 patients.

The results will be reviewed regularly, and if the results are unfavourable, the study will be stopped. If the results are favourable, the sponsor will set up a larger trial, probably double-blind, randomised, and placebo-controlled in design, and with a fixed dose of YF476.

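### The fixed withdrawal limits and the two-subject trigger in 10.4 begin only with the extension; in the first 12 weeks, when every patient is first exposed, withdrawal rests on judgement

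*Protocol*

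**What the plan says.** Section 10.4 contains two regimes.

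- **General rule, whole trial.** It is permissive: "the investigator may withdraw a subject for medical reasons such as intolerance to trial medication". No numerical limit is attached.
- **Extension only.** After "For the extended treatment period, the following criteria apply", withdrawal becomes mandatory for ALT or AST above three times the upper limit of normal; QTc of 500 ms or more, or QT prolongation with a QTc rise of more than 60 ms from baseline; any suspected drug-drug interaction; or an SAE or SUSAR attributable to YF476. The trial-level rule follows directly: "If one of the criteria above is met in 2 or more subjects, dosing will be stopped in all subjects".

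Entry to the extension is conditional (section 9, Extended treatment). The patient must have benefitted from the first 12 weeks "and have tolerated YF476 well, and must give fully informed written consent".

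The dose may rise in both periods. In 14.4 the investigator may "consider increasing the dose to 75 or 100 mg" at Visit 4, and for the extension 11.1 says "The investigator will still have the option to increase the patient's dose to 75 or 100 mg once daily".

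Section 18.2 adds a review that covers the whole trial: "The results will be reviewed regularly, and if the results are unfavourable, the study will be stopped". It does not say what counts as unfavourable.

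**The concern.** The fixed limits protect patients who have already taken YF476 for 12 weeks and tolerated it. They do not cover the period in which intolerance would first appear. The same laboratory or ECG result therefore has different consequences depending on when it occurs, and two such results in the first period cannot trigger the stop. What is at stake is patient safety and consistent handling of a small group. No efficacy endpoint or estimate is affected.

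**Working it through.** The plan states no figure on this point, so there is none to reproduce. The check is of the text, followed by a count and an illustration of what the fix would cost.

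**1. What reaches the first 12 weeks?**

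| Section | Provision | Fixed withdrawal threshold? |
|---|---|---|
| 10.3 | QTc above 450 msec and certain medicines exclude at entry | No, entry only |
| 10.4, general part | Investigator may withdraw for medical reasons | No |
| 11.4 | Withdrawal for concomitant treatment, at discretion | No |
| 12.2 | QTc prolongation is to be looked for | No action attached |
| 16.1, 16.2 | Abnormal results may be classed as adverse, significant or serious events | No, classification and recording |
| 16.3 | All SAEs reported within 24 h; dosing stops if the investigator thinks an SAE justifies it | No |
| 17 | Out-of-range and changed laboratory values are flagged, listed and commented on | No |
| 18.2 | Regular review; stop if unfavourable | Undefined |
| 20.1(b), (h) | Repeat tests on safety concern; higher starting dose for later patients if well tolerated | No |
| 22 | Right to terminate for safety | No |

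**2. The same result in each period.** Take a QTc of 500 ms or an ALT above three times the upper limit.

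- At Visits 3 to 6: withdrawal is optional, and the event does not count towards the two-subject stop.
- In the extension: withdrawal is mandatory, and the event counts.

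**3. How many observations have no limit?** The chart in 6.2 schedules an ECG and safety tests at Visits 3, 4, 5 and 6. Patients with complete regression at Visit 4 skip Visits 5 and 6. With the maximum of 10 patients:

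- all regress at Visit 4: 10 × 2 = 20 patient-visits;
- none do: 10 × 4 = 40 patient-visits.

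**4. What would the limits cost if applied from the first dose?** Let p be an assumed risk that a patient meets any counted criterion, with n = 10 independent patients.

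- Expected withdrawals = 10p.
- P(at least one) = 1 − (1 − p)^10.
- P(two-subject stop) = 1 − (1 − p)^10 − 10p(1 − p)^9.

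For p = 0.02 the last formula gives 1 − 0.8171 − 0.1667 = 0.016.

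| Assumed p | Expected withdrawals | P(at least one) | P(two-subject stop) |
|---|---|---|---|
| 2% | 0.2 | 18.3% | 1.6% |
| 5% | 0.5 | 40.1% | 8.6% |
| 10% | 1.0 | 65.1% | 26.4% |
| 20% | 2.0 | 89.3% | 62.4% |

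The last column counts any criterion. The rule can also be read as needing the same criterion twice. With three independent criteria at p/3 each, 1 − [P(X ≤ 1; 10, p/3)]^3 gives 0.6% at p = 2% and 3.4% at p = 5%.

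**The case against.** **There is a visible rationale.** Section 7.9 says toxicology supports dosing for up to 13 weeks (91 days). The first period lasts 12 weeks (84 days) and lies inside that cover; the 52-week extension does not. This explains why rules were added for the extension. It does not explain having no limit at first exposure.

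**The first period is not unprotected.** A reader might infer that unselected patients are treated without safeguards. They are not. Entry requires good general health and excludes a QTc above 450 msec, and interacting medicines are restricted. A marked ALT rise or a QTc of 500 ms might well be reported as a significant or serious event under 16.1. A competent investigator would probably act on it. All of this stands, but none of it mandates withdrawal.

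**Visit 4.** A reader might infer that 14.4 omits a safety check before a dose increase, because only the branch that stops treatment carries the condition "omit Visits 5 and 6, and proceed to Visit 7, providing all safety assessments prove satisfactory". The text does not support that. The condition governs leaving out two scheduled safety visits, and patients on the other branch keep those visits. Section 14.10 has the same structure at Visit 10, inside the extension, where the fixed limits do apply.

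**Duration of earlier exposure.** A reader might argue that human dosing at 50 mg or more has never exceeded 7 days. Among the completed studies in 7.8.5, the six-week study used 100 mg of a formulation that 7.9 equates to about 15 mg of the present one. But the ongoing 14-day study (7.8.6) reports only its 25 mg result, so its other doses are unknown. The supportive data also count: no ECG effect in dogs over 13 weeks, 25-fold hERG cover, and no ECG or safety-test effects in healthy subjects at up to 200 mg/day for 7 days. The point does not rest on a gap in duration.

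**Reach of the stop.** Only the trigger is limited to the extension. Once triggered, the stop applies to all subjects and so, on its face, to patients still in their first 12 weeks.

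**Conclusion.** The point holds and should be fixed. The mandatory criteria and the two-subject trigger in 10.4 are confined to the extension, and nothing else in the protocol sets a withdrawal threshold for the first 12 weeks. The reading of the text is secure.

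The size can be given only as 20 to 40 patient-visits with ECG and liver results to which no limit applies, assuming 10 patients who attend as scheduled. The protocol gives no rate at which patients would meet these limits, so no probability of harm is claimed. The stopping probabilities above rest on assumed rates and independence between patients.

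**What to change.** Amend 10.4 as follows.

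- From the first dose, withdraw patients who meet the existing ALT/AST, QTc or attributable SAE/SUSAR criterion. Define QTc baseline as the Visit 1 ECG, the only scheduled ECG before dosing (6.2).
- Keep the suspected-interaction criterion for the extension. In the first 12 weeks manage suspected interactions as in Appendix 1, which relies on adjusting or substituting the other medicine.
- Count events in both periods towards the two-subject stop.

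This is more than a change of scope: it defines the baseline, leaves one criterion out of the first period and adds counting across periods. Section 14.4 needs no separate change, because a patient who meets a criterion at or before Visit 4 would be withdrawn under 10.4.

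The cost is one protocol amendment. ECGs, liver tests and adverse events are already collected at Visits 3 to 6. The real downside, in a rare disease with at most 10 patients, is that a patient who might have continued is withdrawn, or that dosing stops for all. That is unlikely if the true risk is near 2% and likely if it is near 20%, when a pause would be wanted.
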